## 6.2.2. Safety

### 6.2.2.1. Adverse Events of Special Interest

Cardiovascular (CV) AEs, gastrointestinal (GI) AEs, *C. difficile* AEs, and AEs related to Acetylcholinesterase Inhibition (AChE-I) as determined by algorithm will be considered AESIs.

#### ***Clostridium difficile* AESIs**

AEs will be regarded as *C. difficile* AESIs if the preferred terms are either *Clostridium difficile* infection or *Clostridium difficile* colitis.

**Cardiovascular and Gastrointestinal AESIs**

Gastrointestinal AESIs are defined as AEs with a "Gastrointestinal disorders" SOC. AEs will be regarded as Cardiovascular AESIs if the preferred terms are any one of the following PTs below. Term	Code	Term	Code
Degenerative aortic valve disease	10075846	Tachycardia	10043071
Supraventricular extrasystoles	10042602	Ventricular tachyarrhythmia	10065341
Rebound tachycardia	10067207	Torsade de pointes	10044066
Cardio-respiratory arrest neonatal	10007618	Fascicular block	10086740
Cardiac flutter	10052840	Lown-Ganong-Levine syndrome	10024984
Paroxysmal arrhythmia	10050106	Conduction disorder	10010276
Cardiac death	10049993	Congenital supraventricular tachycardia	10082343
Atrial conduction time prolongation	10064191	Pacemaker generated arrhythmia	10053486
Neonatal bradyarrhythmia	10082054	Wolff-Parkinson-White syndrome	10048015
Bradycardia foetal	10006094	Long QT syndrome	10024803
Neonatal sinus bradycardia	10082188	Parasystole	10033929
Sinus bradycardia	10040741	Cardiac arrest neonatal	10007516
Marshall-White syndrome	10088084	Foetal tachyarrhythmia	10077575
Junctional ectopic tachycardia	10074640	Neonatal sinus tachycardia	10082191
Ventricular fibrillation	10047290	Congenital tricuspid valve stenosis	10010656
Ventricular parasystole	10058184	Parachute mitral valve	10064192
Pulseless electrical activity	10058151	Stroke in evolution	10059613
Accessory cardiac pathway	10067618	Subarachnoid haemorrhage	10042316
Sinoatrial block	10040736	Ischaemic cerebral infarction	10060840
Paroxysmal atrioventricular block	10077503	Spinal subdural haematoma	10050164
Ogden syndrome	10082376	Thrombotic stroke	10043647
Familial atrial fibrillation	10088317	Pituitary infarction	10035092
Nodal rhythm	10029470	Cerebral haemorrhage neonatal	10008112
Bundle branch block left	10006580	Cerebral haemorrhage	10008111
Precerebral artery embolism	10085250	Claude's syndrome	10085447
Cerebral septic infarct	10070671	Vertebrobasilar stroke	10082484
Cerebellar ischaemia	10068621	Intraoperative cerebral artery occlusion	10056382
Pseudostroke	10078090	Cerebral gas embolism	10070813
Basal ganglia stroke	10071043	Brain stem thrombosis	10062573
Lacunar infarction	10051078	Basal ganglia haemorrhage	10067057
Ruptured cerebral aneurysm	10039330	Vertebral artery perforation	10075735
Malignant middle cerebral artery syndrome	10086546	Carotid artery perforation	10075728
Cerebral artery perforation	10075734	Ischaemic stroke	10061256

Gastrointestinal AESIs are defined as AEs with a "Gastrointestinal disorders" SOC. AEs will be regarded as Cardiovascular AESIs if the preferred terms are any one of the following PTs below. Term	Code	Term	Code
Spinal cord haemorrhage	10048992	Cerebral arteriovenous malformation haemorrhagic	10008086
Subarachnoid haematoma	10076701	Cerebrovascular disorder	10008196
Mitral valve disease	10061532	Myxomatous mitral valve degeneration	10077377
Pulmonary oil microembolism	10069388	Mitral valve stenosis	10027733
Heritable pulmonary arterial hypertension	10085244	Pulmonary tumour thrombotic microangiopathy	10079988
Cor pulmonale acute	10010969	Pulmonary venous thrombosis	10037459
Neonatal pulmonary hypertension	10088909	Cement embolism	10050484
Pulmonary hypertensive crisis	10068726	Pulmonary veno-occlusive disease	10037458
Pulmonary valve incompetence	10037448	Newborn persistent pulmonary hypertension	10053592
Transient aphasia	10080106	Pulmonary valve thickening	10079337
Subclavian steal syndrome	10042335	Capsular warning syndrome	10067744
Tricuspid valve thrombosis	10088062	Tricuspid valve incompetence	10044640
Tricuspid valve disease mixed	10086096	Transmyocardial revascularisation	10059211
Heart valve stenosis	10061996	Deep vein thrombosis postoperative	10066881
Peripheral revascularisation	10053351	Carotid revascularisation	10072559
Respiratory sinus arrhythmia magnitude increased	10079115	Progressive encephalopathy, hypsarrhythmia and optic atrophy syndrome	10086607
Renal artery revascularisation	10087816	Unicuspid aortic valve	10081548
Acute myocardial infarction	10000891	Aortic valve atresia	10066801
Aortic valve disease	10061589	Arrhythmia supraventricular	10003130
Congenital aortic valve incompetence	10010370	Reperfusion arrhythmia	10058156
Supravalvular aortic stenosis	10042598	Heart alternation	10058155
Arrhythmia neonatal	10003124	Timothy syndrome	10079205
Central bradycardia	10078310	Foetal heart rate disorder	10061158
Sinus arrest	10040738	Atrial parasystole	10071666
Cardiac fibrillation	10061592	Atrial tachycardia	10003668
Trifascicular block	10044644	Bifascicular block	10057393
Accelerated idioventricular rhythm	10049003	Sudden cardiac death	10049418
Ventricular tachycardia	10047302	Atrioventricular block complete	10003673
Bundle branch block right	10006582	Sinus node dysfunction	10075889
Bundle branch block bilateral	10006579	Sudden death	10042434
Bezold-Jarisch reflex	10076999	Cardio-respiratory arrest	10007617
Chronotropic incompetence	10068627	Neonatal tachyarrhythmia	10082055

Gastrointestinal AESIs are defined as AEs with a "Gastrointestinal disorders" SOC. AEs will be regarded as Cardiovascular AESIs if the preferred terms are any one of the following PTs below. Term	Code	Term	Code
Baseline foetal heart rate variability disorder	10074638	Bradycardia	10006093
Inherited cardiac conduction disorder	10070294	Congenital heart valve incompetence	10077594
Ventricular flutter	10047294	Mitral valve atresia	10066800
Straddling tricuspid valve	10083223	Congenital tricuspid valve incompetence	10067887
Extrainschaemic cerebral haematoma	10080347	Congenital heart valve disorder	10064086
Central nervous system haemorrhage	10072043	Congenital tricuspid valve atresia	10049767
Vertebral artery thrombosis	10057777	Cerebral microembolism	10078311
Vertebral artery occlusion	10048965	Carotid aneurysm rupture	10051328
Pituitary haemorrhage	10049760	Cerebral artery occlusion	10008089
Thalamic infarction	10064961	Cerebellar infarction	10008034
Cerebellar artery occlusion	10053633	Cerebral microinfarction	10083668
Reversible ischaemic neurological deficit	10050496	Post stroke depression	10070606
Cerebral infarction foetal	10008119	Precerebral artery thrombosis	10074717
Brain stem haemorrhage	10006145	Brain stem infarction	10006147
Medullary compression syndrome	10087065	Basal ganglia haematoma	10077031
Lacunar stroke	10076994	Mitral valve incompetence	10027727
Emolic cerebellar infarction	10084072	Pulmonary thrombosis	10037437
Cerebral artery embolism	10008088	Pulmonary microemboli	10037421
Embolism arterial	10014513	Hoigne's syndrome	10059393
Mitral valve calcification	10050558	Post procedural pulmonary embolism	10063909
Systolic anterior motion of mitral valve	10076976	Cor pulmonale	10010968
Pulmonary embolism	10037377	Pulmonary arterial hypertension	10064911
Emolic pneumonia	10065680	Pulmonary artery wall hypertrophy	10063561
Cor pulmonale chronic	10010970	Right ventricular hypertension	10074301
Lamb's excrescences	10083691	Tricuspid valve disease	10061389
Arrhythmia prophylaxis	10051305	Cardiac valve rupture	10068165
ECG signs of myocardial infarction	10075299	Heart valve calcification	10058968
Bicuspid aortic valve	10004552	Cardiac valve discolouration	10079467
Arrhythmia	10003119	Cardiac valve vegetation	10057651
Atrioventricular node dysfunction	10084085	Cerebral revascularisation	10071508
Ventricular pre-excitation	10049761	Aortic valve stenosis	10002918
Supraventricular tachyarrhythmia	10065342	Tachyarrhythmia	10049447
Cardiac arrest	10007515	Sinus arrhythmia	10040739
Atrioventricular node dispersion	10077893	Atrioventricular conduction time shortened	10068180
Holiday heart syndrome	10083709	Postural orthostatic tachycardia syndrome	10063080
Anomalous atrioventricular excitation	10002611	Supraventricular tachycardia	10042604

Gastrointestinal AESIs are defined as AEs with a "Gastrointestinal disorders" SOC. AEs will be regarded as Cardiovascular AESIs if the preferred terms are any one of the following PTs below. Term	Code	Term	Code
Bundle branch block	10006578	Sinusoidal foetal heart rate pattern	10074643
Adams-Stokes syndrome	10001115	Bradyarrhythmia	10049765
Atrioventricular dissociation	10069571	Withdrawal arrhythmia	10047997
Atrial escape rhythm	10085756	Tachycardia paroxysmal	10043079
Atrial flutter	10003662	Wandering pacemaker	10047818
Cardiac failure congestive	10007559	Sinus tachycardia	10040752
Bicuspid pulmonary valve	10063730	Arrhythmic storm	10067339
Weber's syndrome	10085448	Ictal bradycardia syndrome	10088979
Cerebral haemorrhage foetal	10050157	Foetal heart rate acceleration abnormality	10074642
Spinal epidural haematoma	10050162	Pacemaker syndrome	10051994
Basal ganglia infarction	10069020	Atrial standstill	10087237
Cerebellar embolism	10067167	Congenital pulmonary valve disorder	10061075
Spinal subarachnoid haemorrhage	10073564	Congenital pulmonary valve atresia	10052644
Septic cerebral embolism	10086435	Congenital mitral valve stenosis	10010548
Intracranial tumour haemorrhage	10022775	Thalamic stroke	10087626
Post procedural stroke	10066591	Basilar artery perforation	10075736
Embolic cerebral infarction	10060839	Brain stem embolism	10074422
Meningorrhagia	10052593	Lateral medullary syndrome	10024033
Intraventricular haemorrhage neonatal	10022841	Occipital lobe stroke	10089110
Cerebellar haemorrhage	10008030	Intracranial haemorrhage neonatal	10086946
Internal capsule infarction	10083408	Pseudo-occlusion of internal carotid artery	10085779
Pituitary apoplexy	10056447	Cerebral vascular occlusion	10076895
Cerebellar artery thrombosis	10008023	Perinatal stroke	10073945
Brain stem stroke	10068644	Cerebral artery thrombosis	10008092
Mitral valve thickening	10079336	Periventricular haemorrhage neonatal	10076706
Ischaemic mitral regurgitation	10077864	Spinal epidural haemorrhage	10049236
Mitral perforation	10068138	Middle cerebral artery stroke	10027580
Portopulmonary hypertension	10067281	Intraventricular haemorrhage	10022840
Right-to-left cardiac shunt	10076605	Haemorrhagic cerebral infarction	10019005
Congenital pulmonary hypertension	10050701	Cerebral infarction	10008118
Pulmonary valve calcification	10057464	Thrombotic cerebral infarction	10067347
Pulmonary valve disease	10061541	Basilar artery thrombosis	10063093
Pulmonary valve sclerosis	10057465	Myocardial infarction	10028596
Pulmonary valve stenosis	10037450	Septic pulmonary embolism	10083093
Tricuspid valve prolapse	10066862	Alveolar capillary dysplasia	10077023
Prosthetic cardiac valve thrombosis	10063176	Coronary sinus dilatation	10082615
Heart valve incompetence	10067660	Pulmonary venous hypertension	10085364

Gastrointestinal AESIs are defined as AEs with a "Gastrointestinal disorders" SOC. AEs will be regarded as Cardiovascular AESIs if the preferred terms are any one of the following PTs below. Term	Code	Term	Code
Cardiac valve disease	10061406	Amaurosis fugax	10001903
Prosthetic cardiac valve regurgitation	10087802	Tricuspid valve sclerosis	10057467
Cardiac valve fatty infiltration	10087637	Tricuspid valve thickening	10079338
Deep vein thrombosis	10051055	Cardiac valve thickening	10079587
Periprocedural myocardial infarction	10079319	Silent myocardial infarction	10049768
Cerebrovascular pseudoaneurysm	10084087	Coronary revascularisation	10049887
Revascularisation procedure	10084091	Foetal cerebrovascular disorder	10053601
Angina unstable	10002388	Aortic annulus rupture	10079586
Aortic valve prolapse	10057454	Subvalvular aortic stenosis	10042431
Aortic valve thickening	10075851	Heart block congenital	10019263
Aortic valve sclerosis	10002917	Extrasystoles	10015856
Williams syndrome	10049644	Atrioventricular block second degree	10003677
Ventricular extrasystoles	10047289	Brugada syndrome	10059027
Ectopic atrial rhythm	10088339	Wolff-Parkinson-White syndrome	10049291
congenital			
Lenegre's disease	10071710	BRASH syndrome	10084073
Nodal arrhythmia	10029458	Ventricular arrhythmia	10047281
Foetal cardiac arrest	10084280	Early repolarisation syndrome	10086230
Rhythm idioventricular	10039111	Foetal heart rate deceleration abnormality	10074636
Atrioventricular block	10003671	Long QT syndrome congenital	10057926
Nonreassuring foetal heart rate pattern	10074641	Agonal rhythm	10054015
Ventricular asystole	10047284	Chronic atrial and intestinal dysrhythmia	syndrome
Defect conduction intraventricular	10012118	Frederick's syndrome	10082089
Tachycardia foetal	10043074	Bradycardia neonatal	10056471
Atrial fibrillation	10003658	Shone complex	10066802
Foetal arrhythmia	10016847	Pulmonary valve stenosis congenital	10037451
Atrioventricular block first degree	10003674	Ebstein's anomaly	10014075
Neonatal tachycardia	10049775	Carotid artery occlusion	10048964
Mitral valve dysplasia	10089005	Cerebellar haematoma	10061038
Congenital mitral valve incompetence	10010547	Spinal cord infarction	10058571
Carotid blowout syndrome	10088005	Migrainous infarction	10056237
Brain stem haematoma	10073230	Cerebral haematoma	10053942
Spinal stroke	10082031	Haemorrhage intracranial	10018985
Putamen haemorrhage	10058940	Embolic stroke	10014498
Carotid artery thrombosis	10007688	Parietal lobe stroke	10089109
Spinal subdural haemorrhage	10073563	Spinal cord haematoma	10076051

Gastrointestinal AESIs are defined as AEs with a "Gastrointestinal disorders" SOC. AEs will be regarded as Cardiovascular AESIs if the preferred terms are any one of the following PTs below. Term	Code	Term	Code
Basilar artery occlusion	10048963	Haemorrhagic transformation stroke	10055677
Cerebellar stroke	10079062	Precerebral artery occlusion	10036511
Inner ear infarction	10070754	Brain stem ischaemia	10006148
Cerebral ischaemia	10008120	Cerebral aneurysm perforation	10075394
Benedikt's syndrome	10085451	Thalamus haemorrhage	10058939
Intracranial haematoma	10059491	Carotid arterial embolus	10007684
Haemorrhagic stroke	10019016	Subdural haemorrhage neonatal	10042365
Cerebral thrombosis	10008132	Subarachnoid haemorrhage neonatal	10042317
Mitral valve disease mixed	10027724	Haemorrhagic cerebellar infarction	10085944
Degenerative mitral valve disease	10075847	Cerebrovascular accident	10008190
Metastatic pulmonary embolism	10069909	Mitral valve sclerosis	10051538
Carcinoid heart disease	10069010	Mitral face	10073380
Cardiac valve replacement complication	10053748	Mitral valve prolapse	10027730
Degenerative multivalvular disease	10081779	Obstetrical pulmonary embolism	10029925
Cardiac valve sclerosis	10061082	Anaphylactoid syndrome of pregnancy	10067010
Cardiac valve abscess	10064267	Pulmonary artery thrombosis	10037340
Respiratory sinus arrhythmia magnitude	10079114	Pulmonary hypertension	10037400
Respiratory sinus arrhythmia magnitude abnormal	10079117	Transient ischaemic attack	10044390
Congenital aortic valve stenosis	10010371	Tricuspid valve stenosis	10044642
Aortic valve calcification	10050559	Degenerative tricuspid valve disease	10078909
Aortic valve incompetence	10002915	Tricuspid valve calcification	10057466
Heyde's syndrome	10049251	Post procedural myocardial infarction	10066592
Aortic valve disease mixed	10002912	Respiratory sinus arrhythmia magnitude decreased	10079116
-	-	Arterial revascularisation	10084482

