2.3.1. Risk Assessment

Potential Risk of Clinical Significance	Summary of Data/Rationale for Risk	Mitigation Strategy
Gepotidacin (GSK2140944)		

Cardiovascular Effects Based on nonclinical data, cardiovascular effects were reversible increase in heart rate and blood pressure (dog and monkey); reversible 10 to 21 msec (4% to 9%) increase in QTc (monkey); and at the highest dose, a reversible 2 to 3 msec (6% to 8%) increase in QRS (monkey). Based on a thorough QTc clinical study, gepotidacin may cause mild, reversible heart rate effects and QT prolongation.
	
In a thorough QTc study, infusion of gepotidacin at doses of 1000 and 1800 mg over 2 hours caused a mild increased heart rate effect of approximately 6 to 10 bpm and QT prolongation measured as $\Delta\Delta QTcF$ of 12 to 22 msec. The QT prolongation evolved during the infusion and was quickly reversed over 2 hours after the end of the infusion (see the IB for details). In Phase I studies, concentration-dependent QT prolongation has been observed during clinical trials with gepotidacin; however, this increase has not translated into clinically significant QTc values or changes from baseline (change from baseline >60 msec or QTcF >500 msec) or cardiovascular AEs. In Phase I and II studies, gepotidacin did not have a clinically relevant effect on cardiac conduction (PR and QRS intervals). Although there appears to be a trend to higher gepotidacin systemic exposure in healthy Japanese compared to Western subjects, the higher systemic exposure of gepotidacin observed in Japanese subjects is currently considered to be within the tolerable range and not associated with any cardiovascular safety concerns.
	
See Section 5.2 for excluded cardiac conditions. Close monitoring of clinical parameters and AEs (Section 1.3) will be conducted, and treatment monitoring and evaluation criteria (Section 7.1.2) will be utilized to mitigate cardiovascular effects. Participants taking medications known to increase QT or potent CYP3A4 inhibitors will be excluded (see Section 6.8.2). See also the Renal and Hepatic sections within this table below.

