
Acetylcholinesterase Inhibition In vitro testing showed gepotidacin to be a rapidly reversible inhibitor of acetylcholinesterase in the clinical plasma concentration range.
 
Based on clinical data, caution should be used in participants who have a condition requiring treatment with anticholinergic medications or who have certain medical conditions that may be exacerbated by the acetylcholinesterase inhibition activity of gepotidacin.
	
Increased cholinergic effects can potentially be associated with more severe symptoms including atrioventricular block, seizure/convulsions, bronchospasm, and vasovagal syncope. No causal relationship between these events and the use of gepotidacin has been established during clinical trials to date.
 
Adverse events consistent with acetylcholinesterase inhibition, including diarrhea, nausea, vomiting, gastrointestinal cramping and pain, dyspnea, bradycardia, lacrimation, salivation, dysarthria, and diaphoresis/sweating have been reported during clinical trials with gepotidacin.
 
Mild and transient non-gastrointestinal AEs have been associated with Cmax levels higher than this dosing regimen.
	
Participants who have medical conditions or require medications that may be impacted by inhibition of acetylcholinesterase will be excluded from participation in this study. See Section 5.2 for excluded medical conditions and Section 6.8.2, Prohibited Medications and Nondrug Therapies, for prohibited medications.
 
Close monitoring of clinical parameters and AEs will be conducted to assess effects potentially related to acetylcholinesterase inhibition (Section 1.3).

Hepatic Effects In preclinical studies, increases in ALT, GLDH, alkaline phosphatase, and total bilirubin were observed in some rat studies of varying exposure.
	
Elevations in ALT have occurred in a few participants with pre-existing hepatitis C infection, but none were felt related to study treatment. The type and pattern of elevation in liver transaminases observed has not been suggestive of an adverse effect of gepotidacin and none were considered related to study treatment.
	
Participants with severe hepatic impairment are excluded from Phase III trials. See Section 5.2 for excluded medical conditions. Monitoring and stopping criteria liver events have been implemented.

Potential Risk of Clinical Significance	Summary of Data/Rationale for Risk	Mitigation Strategy

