To investigate the possibility that the dosage and administration of gepotidacin (1500 mg orally BID for 5 days) specified in global phase III studies (Studies 204989 and 212390) may affect the dosage regimen in Japanese patients, a PK-PD study was conducted from the viewpoints of efficacy evaluation and safety evaluation. From the viewpoint of

efficacy evaluation, the overall probability of target attainment in Japanese subjects considering the percentage of actual MICs is as high as 99.9% for $fAUC_{0-24hr}/MIC = 41.3$ in urine and 96.1% for $fAUC_{0-24hr}/MIC = 275$ in urine (related to resistance suppression), which is also expected to be effective in Japanese subjects. From the viewpoint of safety evaluation, the predicted plasma concentration after twice-daily administration of gepotidacin 1500 mg to Japanese subjects is below the concentration associated with mild transient adverse events (such as salivation, blurred vision, and slurred speech) in previous studies, and the predicted $\Delta\Delta\Delta QTcF$ in the Japanese population is below the value observed in previous intravenous and oral studies in which clinically relevant QTc changes were reported. Therefore, it is considered safe in Japanese subjects. Based on the above, it is appropriate to apply the dosage and administration of gepotidacin (1500 mg orally BID for 5 days) used in global phase III studies (Studies 204989 and 212390) to the Japanese study (Study 214144).

In conclusion, minimum urine levels of gepotidacin are anticipated to be in excess of the $fAUC/MIC$ target necessary for both efficacy and resistance suppression for *E. coli* as determined from the in vitro PK/PD models. Given that the bladder is the primary site of infection in cystitis, the use of gepotidacin urine PK data, coupled with the robust in vivo efficacy demonstrated in the Phase IIa acute uncomplicated cystitis study and human simulated PK pyelonephritis model, is appropriate for selecting the gepotidacin 1500 mg BID oral dose for 5 days for study in the treatment of participants with acute uncomplicated cystitis.

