8.3.7. Adverse Events of Special Interest

Predefined AEs of special interest for this study are CV events, gastrointestinal events, *C. difficile* infection or colitis events, and AEs related to acetylcholinesterase inhibition (see Section 2.3.1), which will be identified by a prespecified list of coded terms or determined by algorithm, as described in the Statistical Analysis Plan (SAP).

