### **Time of onset (hours):**

#### **1. Definition**

Time of onset (hours) is defined as time from first dose to the start date of the first event in hours. The first event is defined as the treatment emergent AE of which start date is the earliest within each participant. If the start time of the first event is missing, 00:00 will be imputed to calculate the time of onset. Time of onset will be rounded to the nearest hour, which will be zero hour if time of onset is <30 minutes.

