### Acetylcholinesterase Inhibition AESIs

AEs will be regarded as Acetylcholinesterase Inhibition AESIs if the preferred terms are any one of the following PTs below.

Term	Code	Term	Code
Atrioventricular block first degree	10003674	Convulsions local	10010920
Atonic seizures	10003628	Diarrhoea	10012735
Bradycardia foetal	10006094	Status epilepticus	10041962
Diarrhoea haemorrhagic	10012741	Laryngeal dyspnoea	10052390
Dysarthria	10013887	Prophylaxis against bronchospasm	10054927

Term	Code	Term	Code
Dyspnoea paroxysmal nocturnal	10013974	Post procedural diarrhoea	10057585
Retching	10038776	Procedural vomiting	10066963
Simple partial seizures	10040703	Idiopathic generalised epilepsy	10071081
Sinus bradycardia	10040741	Bradycardia	10006093
Vomiting projectile	10047708	Convulsive threshold lowered	10010927
Self-induced vomiting	10048636	Diarrhoea infectious neonatal	10012744
Hypoglycaemic seizure	10048803	Dyspnoea at rest	10013969
Lennox-Gastaut syndrome	10048816	Frequent bowel movements	10017367
Nocturnal dyspnoea	10049235	Haematemesis	10018830
Atypical benign partial epilepsy	10056699	Nausea	10028813
Hyponatraemic seizure	10073183	Tonic convulsion	10043994
Infantile vomiting	10075315	Frontal lobe epilepsy	10049424
Neonatal sinus bradycardia	10082188	Tonic clonic movements	10051171
Abdominal discomfort	10000059	Clonic convulsion	10053398
Defaecation urgency	10012110	Lafora's myoclonic epilepsy	10054030
Drooling	10013642	Psychogenic seizure	10058895
Epilepsy	10015037	Partial seizures	10061334
Flatulence	10016766	Seizure like phenomena	10071048
Heart rate decreased	10019301	Change in seizure presentation	10075606
Hyperkinesia	10020651	Idiopathic partial epilepsy	10076552
Petit mal epilepsy	10034759	Post stroke seizure	10076981
Psychomotor hyperactivity	10037211	Abdominal pain lower	10000084
Vomiting	10047700	Cold sweat	10009866
Myoclonic epilepsy	10054859	Diarrhoea infectious	10012742
Partial seizures with secondary generalisation	10056209	Dyspnoea exertional	10013971
Alcoholic seizure	10056347	Febrile convulsion	10016284
Therapeutic emesis	10058324	Generalised tonic-clonic seizure	10018100
Faecal vomiting	10064670	Night sweats	10029410
Psychogenic pseudosyncope	10075190	Presyncope	10036653
Central bradycardia	10078310	Sweat gland disorder	10042653
Gastrointestinal disorder	10017944	Bradyarrhythmia	10049765
Hyperemesis gravidarum	10020614	Convulsion in childhood	10052391
Lacrimation decreased	10023642	Prophylaxis of nausea and vomiting	10054133

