## 6.2.9. Handling of Partial Dates

Element	Reporting Detail									
General	
 
Partial dates will be displayed as captured in participant listing displays.
 
However, where necessary, display macros may impute dates as temporary variables for sorting data in listings only. In addition, partial dates may be imputed for 'slotting' data to study phases or for specific analysis purposes as outlined below.
 
Imputed partial dates will not be used to derive study day, time to onset or duration (e.g., time to onset or duration of adverse events), or elapsed time variables (e.g., time since diagnosis). In addition, imputed dates are not used for deriving the last contact date in overall survival analysis dataset.
 
									
Adverse Events	
 
Partial dates for AE recorded in the CRF will be imputed using the following conventions:
 
 
 
 Missing start time (AChE-I only)	Midnight 0:00:00 will be used for AEs with missing start time to determine if it's AChE-I.	
 
		Missing start time (AChE-I only)	Midnight 0:00:00 will be used for AEs with missing start time to determine if it's AChE-I.						
Missing start time (AChE-I only)	Midnight 0:00:00 will be used for AEs with missing start time to determine if it's AChE-I.									

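### The SAP's AESI rules do not fully match the risks in protocol 2.3.1: no ECG QT-prolongation term in the cardiovascular list, only first-degree AV block in the AChE-I list, and a midnight imputation that gives a negative onset time on the first-dose day

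*SAP*

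**What the plan says.** Occurrence of AESIs is part of a secondary safety endpoint (protocol section 3, SAP 1.1). Protocol 8.3.7 names four types: cardiovascular, gastrointestinal, *C. difficile*, and "AEs related to acetylcholinesterase inhibition (see Section 2.3.1), which will be identified by a prespecified list of coded terms" or by an algorithm. It leaves the detail to the SAP.

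- **Cardiovascular.** SAP 6.2.2.1: "AEs will be regarded as Cardiovascular AESIs if the preferred terms are any one of the following PTs below". Protocol 2.3.1, in its cardiovascular row, says that "gepotidacin may cause mild, reversible heart rate effects and QT prolongation".
- **AChE-I.** SAP 6.2.2.1 gives a second closed list, whose only AV block entry is "Atrioventricular block first degree". Protocol 2.3.1 says that increased cholinergic effects can "potentially be associated with more severe symptoms including atrioventricular block", with no degree stated. SAP 4.6.2.1 adds a timing condition (start no later than 12 hours after the latest dose) and a cumulative grade score that sums the grades of a participant's AChE-I events.
- **Missing start times.** SAP 4.6.2.1, time of onset: "If the start time of the first event is missing, 00:00 will be imputed to calculate the time of onset". SAP 6.2.9 uses the same value for classification: "Midnight 0:00:00 will be used for AEs with missing start time to determine if" the event is AChE-I.

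**The concern.** Both lists are closed, so a preferred term that is not on the list is not counted in that category. Three consequences follow.

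1. Protocol 7.1.2 and 8.2.3 require clinically significant ECG changes to be reported as AEs. If such an AE is coded as an ECG finding of QT prolongation, it does not enter the cardiovascular AESI table, although it is a risk that the protocol itself describes.
2. The AChE-I score is meant to reflect severity, yet its list admits the mildest degree of AV block and leaves out the more severe ones.
3. The first dose is given at the site on Day 1 (protocol 6.1), so midnight of that day always precedes it. Time of onset then becomes negative, and the 12-hour rule has no earlier dose to count from.

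At stake is the accuracy of two descriptive AESI summaries and one onset-time summary. No hypothesis test is involved.

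**Working it through.** **1. QT terms.** Reading the cardiovascular list for QT and ECG terms gives Long QT syndrome, Long QT syndrome congenital and Torsade de pointes. The only entry that names the ECG is *ECG signs of myocardial infarction*. There is no ECG QT-prolongation term. SAP 4.6.2.4, by contrast, identifies QT prolongation through the high-level term *ECG investigations*, in a bullet separate from the one that brings in the AESIs of 6.2.2.1. So the SAP expects QT prolongation to be coded where the AESI list does not look.

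**2. AV block terms.** The two lists side by side:

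| Preferred term | CV list | AChE-I list |
|---|---|---|
| First degree | yes | yes |
| Second degree | yes | no |
| Complete | yes | no |
| Unspecified | yes | no |
| Paroxysmal | yes | no |

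Of the 127 AChE-I terms, 1 concerns AV block, and 4 of the 5 AV block terms in the cardiovascular list are absent.

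Effect on the score (hypothetical participant, both events within 12 hours of a dose): Grade 1 nausea and Grade 3 second-degree AV block. Under SAP Table 2, a score of 1 to 3 gives cumulative grade 1, and 4 to 6 gives grade 2.

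- As written: score = 1, cumulative grade 1. Non-GI score = 0, cumulative grade 0.
- With the block counted: score = 1 + 3 = 4, cumulative grade 2. Non-GI score = 3, cumulative grade 1.

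**3. Midnight imputation.** The documents give no clock time for the first dose, so four are assumed. There are 10 doses, 12 hours apart (protocol 6.1 and 6.8.2). With the first dose at hour *h* of Day 1:

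- onset for a Day 1 event with no time = 0 - *h*
- midnight starting Day *d* falls at hour 24(*d* - 1)
- the last dose falls at hour *h* + 12 × 9 = *h* + 108

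| Assumed first dose | Day 1 onset (h) | Hours since latest dose, Days 2 to 6 | Hours since last dose, Day 7 |
|---|---|---|---|
| 08:00 | -8 | 4 | 144 - 116 = 28 |
| 10:00 | -10 | 2 | 144 - 118 = 26 |
| 12:00 | -12 | 0 | 144 - 120 = 24 |
| 15:00 | -15 | 9 | 144 - 123 = 21 |

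On Days 2 to 6 every such event meets the 12-hour limit, so the rule favours inclusion. On Day 7 it does not, and a later true start on that day would not meet it either. Only Day 1 goes wrong: onset is negative, and there is no earlier dose. If *latest dose* means the latest prior dose, the test is undefined. If the wording is taken literally as an upper limit only, the event passes. The flag in the same section for events within 6 hours of the latest dose has the same gap.

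With the first-dose time imputed instead, onset = 0 h and time since dose = 0 h, so the event passes under either reading. That is also the sensible answer: with 12-hourly dosing, any start on Day 1 after the first dose lies within 12 hours of a dose.

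**The case against.** The case for leaving the rules alone is substantial.

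- **QT prolongation is not hidden.** It enters the adverse-reaction short list automatically (SAP 4.6.2.4), worst-case QTc is summarised against set limits (4.6.3.3), and all AEs are tabulated and listed. The reference to Section 2.3.1 in protocol 8.3.7 most naturally belongs to the AChE-I type alone, and the cardiovascular list follows the categories in protocol 10.3.3, which do not name QT prolongation. This stands as mitigation. It does not put the event into the cardiovascular AESI count, and 10.3.3 governs which events need a CRF page.
- **AV block.** A reader might infer that higher-grade block is missed as an AESI. It is not: all five terms are in the cardiovascular list and are summarised by maximum grade. Only the AChE-I category and its score are affected.
- **Day 1 events.** A reader might infer that they are lost. The rule applies only when the time is missing, and SAP 6.2.5.2 then compares dates alone, so the event stays treatment-emergent. Exclusion from AChE-I follows under one reading only. The SAP's remark that an onset under 30 minutes becomes zero might be stretched to negative values, but it reads as a note on rounding.
- **Blurred vision.** It is absent from the AChE-I list, and protocol 4.3 mentions "mild transient adverse events (such as salivation, blurred vision, and slurred speech". A reader might take this as a named AChE-I event. Protocol 2.3.1 does not include it among the events consistent with acetylcholinesterase inhibition, and 4.3 does not attribute it to that mechanism.
- **Three AESI types in the overview (SAP 4.6.2).** This looks like a miscount against four defined types, but it matches the SAP's three headings, which combine cardiovascular and gastrointestinal events.

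Protocol 9.3.4 also promises manual review alongside the programmed rules. The SAP's AESI sections describe only programmed rules, so that review cannot be relied on to close these gaps.

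**Conclusion.** The mismatch is real and minor. As written, an ECG-coded QT-prolongation AE is not a cardiovascular AESI, four AV block terms do not reach the AChE-I category or its score, and a Day 1 event with no start time gets a pre-dose onset (-8 to -15 hours under the assumed dosing times) with an ambiguous AChE-I status. No event disappears from the safety reporting, and the primary analysis is untouched.

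The number of participants affected cannot be derived, because the documents give no event counts and no rate of missing start times. The QT point assumes that such an AE is coded as an ECG finding, as SAP 4.6.2.4 does, and not as Long QT syndrome. Coding of reported terms cannot be checked from the documents.

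**What to change.** Three edits to SAP 6.2.2.1, 4.6.2.1 and 6.2.9, made before unblinding:

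1. Add the ECG QT-prolongation preferred term to the cardiovascular list. Add the preferred term only: by its name, the *ECG investigations* high-level term covers ECG findings in general.
2. Add unspecified, second-degree, complete and paroxysmal AV block, already in the cardiovascular list, to the AChE-I list.
3. For a missing start time on the first-dose date, impute the first-dose time, both for onset and for the AChE-I test. Keep 00:00 on all other dates.

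While the list is open, check *Lacrimation decreased*. Protocol 2.3.1 names lacrimation as a reported effect, so the opposite term is odd, though it can only over-include.

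The cost is two list edits and one changed imputation rule, with no new data. AESI counts may rise slightly. The AChE-I list would then need a note if it is meant to match the one used in the global studies.
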